14.2. Definition of SAE

If an event is not an AE per definition above, then it cannot be an SAE even if serious conditions are met (eg, hospitalization for signs/symptoms of the disease under study, death due to progression of disease).

An SAE is defined as any untoward medical occurrence that, at any dose: Results in death

Is life-threatening

The term "life-threatening" in the definition of "serious" refers to an event in which the patient was at risk of death at the time of the event. It does not refer to an event that hypothetically might have caused death if it were more severe.

Requires inpatient hospitalization or prolongation of existing hospitalization

In general, hospitalization signifies that the patient has been detained (usually involving at least an overnight stay) at the hospital or emergency ward for observation and/or treatment that would not have been appropriate in the physician's office or outpatient setting. Complications that occur during hospitalization are AEs. If a complication prolongs

An SAE is defined as any untoward medical occurrence that, at any dose:

hospitalization or fulfills any other serious criteria, the event is serious. When in doubt as to whether "hospitalization" occurred or was necessary, the AE should be considered serious.

Hospitalization for elective treatment of a preexisting condition that did not worsen from baseline is not considered an AE.

Results in persistent disability/incapacity

- The term disability means a substantial disruption of a person's ability to conduct normal life functions.
- This definition is not intended to include experiences of relatively minor medical significance such as uncomplicated headache, nausea, vomiting, diarrhea, influenza, and accidental trauma (eg, sprained ankle) which may interfere with or prevent everyday life functions but do not constitute a substantial disruption.

Is a congenital anomaly/birth defect

Other situations:

- Medical or scientific judgment should be exercised in deciding whether SAE reporting is appropriate in other situations such as important medical events that may not be immediately lifethreatening or result in death or hospitalization but may jeopardize the patient or may require medical or surgical intervention to prevent one of the other outcomes listed in the above definition. These events should usually be considered serious.
- Examples of such events include invasive or malignant cancers, intensive treatment in an emergency room or at home for allergic bronchospasm, blood dyscrasias or convulsions that do not result in hospitalization, or development of drug dependency or drug abuse.
- Progression of the malignancy under study (including signs and symptoms of progression) should not be reported as an SAE unless the outcome is fatal within the active collection period. Hospitalization due to signs and symptoms of disease progression should not be reported as an SAE. If the malignancy has a fatal outcome during the study or within the active collection period, then the event leading to death must be recorded as an AE on the CRF, and as an SAE with CTCAE Grade 5 (see the Assessment of Intensity section).
- Suspected transmission via a Pfizer product of an infectious agent, pathogenic or non-pathogenic, is considered serious. The event may be suspected from clinical symptoms or laboratory findings indicating an infection in a patient exposed to a Pfizer product. The terms "suspected transmission" and "transmission" are considered synonymous. These cases are considered unexpected and handled as serious expedited cases by pharmacovigilance personnel. Such cases are also considered for reporting as product defects, if appropriate.

14.3. Recording/Reporting and Follow-up of AEs and/or SAEs

AE and SAE Recording/Reporting

The table below summarizes the requirements for recording adverse events on the CRF and for reporting serious adverse events on the CT SAE Report Form to Pfizer Safety. These requirements are delineated for 3 types of events: (1) SAEs; (2) nonserious adverse events (AEs); and (3) exposure to the study treatment under study during pregnancy or breastfeeding, and occupational exposure.

It should be noted that the CT SAE Report Form for reporting of SAE information is not the same as the AE page of the CRF. When the same data are collected, the forms must be completed in a consistent manner. AEs should be recorded using concise medical terminology and the same AE term should be used on both the CRF and the CT SAE Report Form for reporting of SAE information.

| Safety Event | Recorded on the CRF | Reported on the CT SAE Report Form to Pfizer Safety Within 24 Hours of Awareness |
|--|--|---|
| SAE | All | All |
| Nonserious AE | All | None |
| Exposure to the study treatment under study during pregnancy or breastfeeding, and occupational exposure | All AEs/SAEs associated with exposure during pregnancy or breastfeeding Occupational exposure is not recorded. | All (and EDP supplemental form for EDP) Note: Include all SAEs associated with exposure during pregnancy or breastfeeding. Include all AEs/SAEs associated with occupational exposure. |

- When an AE/SAE occurs, it is the responsibility of the investigator to review all documentation (eg, hospital progress notes, laboratory reports, and diagnostic reports) related to the event.
- The investigator will then record all relevant AE/SAE information in the CRF.
- It is **not** acceptable for the investigator to send photocopies of the patient's medical records to Pfizer Safety in lieu of completion of the CT SAE Report Form/AE/SAE CRF page.
- There may be instances when copies of medical records for certain cases are requested by Pfizer Safety. In this case, all patient identifiers, with the exception of

the patient number, will be redacted on the copies of the medical records before submission to Pfizer Safety.

• The investigator will attempt to establish a diagnosis of the event based on signs, symptoms, and/or other clinical information. Whenever possible, the diagnosis (not the individual signs/symptoms) will be documented as the AE/SAE.

Assessment of Intensity

The investigator will make an assessment of intensity for each AE and SAE reported during the study and assign it to 1 of the following categories per CTCAE Version 4.03:

| GRADE | Clinical Description of Severity |
|-------|--|
| 1 | MILD adverse event |
| 2 | MODERATE adverse event |
| 3 | SEVERE adverse event |
| 4 | LIFE-THREATENING consequences; urgent intervention indicated |
| 5 | DEATH RELATED TO adverse event |

Assessment of Causality

- The investigator is obligated to assess the relationship between study treatment and each occurrence of each AE/SAE.
- A "reasonable possibility" of a relationship conveys that there are facts, evidence, and/or arguments to suggest a causal relationship, rather than a relationship cannot be ruled out.
- The investigator will use clinical judgment to determine the relationship.
- Alternative causes, such as underlying disease(s), concomitant therapy, and other risk factors, as well as the temporal relationship of the event to study treatment administration, will be considered and investigated.
- The investigator will also consult the IB and/or product information, for marketed products, in his/her assessment.
- For each AE/SAE, the investigator must document in the medical notes that he/she has reviewed the AE/SAE and has provided an assessment of causality.
- There may be situations in which an SAE has occurred and the investigator has minimal information to include in the initial report to the sponsor. However, it is very important that the investigator always make an assessment of causality for every event before the initial transmission of the SAE data to the sponsor.

Assessment of Causality

- The investigator may change his/her opinion of causality in light of followup information and send an SAE followup report with the updated causality assessment.
- The causality assessment is one of the criteria used when determining regulatory reporting requirements.
- If the investigator does not know whether or not the study treatment caused the event, then the event will be handled as "related to study treatment" for reporting purposes, as defined by the sponsor. In addition, if the investigator determines that an SAE is associated with study procedures, the investigator must record this causal relationship in the source documents and CRF, and report such an assessment in the dedicated section of the CT SAE Report Form and in accordance with the SAE reporting requirements.

Follow-up of AEs and SAEs

- The investigator is obligated to perform or arrange for the conduct of supplemental measurements and/or evaluations as medically indicated or as requested by the sponsor to elucidate the nature and/or causality of the AE or SAE as fully as possible. This may include additional laboratory tests or investigations, histopathological examinations, or consultation with other healthcare providers.
- New or updated information will be recorded in the originally completed CRF.
- The investigator will submit any updated SAE data to the sponsor within 24 hours of receipt of the information.

14.4. Reporting of SAEs

SAE Reporting to Pfizer Safety via CT SAE Report Form

- Facsimile transmission of the CT SAE Report Form is the preferred method to transmit this information to Pfizer Safety.
- In circumstances when the facsimile is not working, notification by telephone is acceptable with a copy of the CT SAE Report Form sent by overnight mail or courier service.
- Initial notification via telephone does not replace the need for the investigator to complete and sign the CT SAE Report Form pages within the designated reporting time frames.

15. APPENDIX 5: LIVER SAFETY: SUGGESTED ACTIONS AND FOLLOW-UP ASSESSMENTS

Potential Cases of Drug-Induced Liver Injury

Humans exposed to a drug who show no sign of liver injury (as determined by elevations in transaminases) are termed "tolerators," while those who show transient liver injury, but adapt are termed "adaptors." In some patients, transaminase elevations are a harbinger of a more serious potential outcome. These patients fail to adapt and therefore are "susceptible" to progressive and serious liver injury, commonly referred to as DILI. Patients who experience a transaminase elevation above 3 × ULN should be monitored more frequently to determine if they are an "adaptor" or are "susceptible."

In the majority of DILI cases, elevations in AST and/or ALT precede TBili elevations (> $2 \times$ ULN) by several days or weeks. The increase in TBili typically occurs while AST/ALT is/are still elevated above $3 \times$ ULN (ie, AST/ALT and TBili values will be elevated within the same laboratory sample). In rare instances, by the time TBili elevations are detected, AST/ALT values might have decreased. This occurrence is still regarded as a potential DILI. Therefore, abnormal elevations in either AST OR ALT in addition to TBili that meet the criteria outlined below are considered potential DILI (assessed per Hy's law criteria) cases and should always be considered important medical events, even before all other possible causes of liver injury have been excluded.

The threshold of laboratory abnormalities for a potential DILI case depends on the patient's individual baseline values and underlying conditions. Patients who present with the following laboratory abnormalities should be evaluated further as potential DILI (Hy's law) cases to definitively determine the etiology of the abnormal laboratory values:

- Patients with AST/ALT and TBili baseline values within the normal range who subsequently present with AST OR ALT values >3 × ULN AND a TBili value >2 × ULN with no evidence of hemolysis and an alkaline phosphatase value <2 × ULN or not available.
- For patients with baseline AST **OR** ALT **OR** TBili values above the ULN, the following threshold values are used in the definition mentioned above, as needed, depending on which values are above the ULN at baseline:
 - Preexisting AST or ALT baseline values above the normal range: AST or ALT values >2 times the baseline values AND >3 × ULN; or >8 × ULN (whichever is smaller).
 - Preexisting values of TBili above the normal range: TBili level increased from baseline value by an amount of at least 1 × ULN or if the value reaches >3 × ULN (whichever is smaller).

Rises in AST/ALT and TBili separated by more than a few weeks should be assessed individually based on clinical judgment; any case where uncertainty remains as to whether it represents a potential Hy's law case should be reviewed with the sponsor.

Version 5

The patient should return to the investigator site and be evaluated as soon as possible, preferably within 48 hours from awareness of the abnormal results. This evaluation should include laboratory tests, detailed history, and physical assessment.

In addition to repeating measurements of AST and ALT and TBili for suspected cases of Hy's law, additional laboratory tests should include albumin, CK, direct and indirect bilirubin, GGT, PT/INR, total bile acids, and alkaline phosphatase. Consideration should also be given to drawing a separate tube of clotted blood and an anticoagulated tube of blood for further testing, as needed, for further contemporaneous analyses at the time of the recognized initial abnormalities to determine etiology. A detailed history, including relevant information, such as review of ethanol, acetaminophen/paracetamol (either by itself or as a coformulated product in prescription or over-the-counter medications), recreational drug, supplement (herbal) use and consumption, family history, sexual history, travel history, history of contact with a jaundiced person, surgery, blood transfusion, history of liver or allergic disease, and potential occupational exposure to chemicals, should be collected. Further testing for acute hepatitis A, B, C, D, and E infection and liver imaging (eg, biliary tract) and collection of serum samples for acetaminophen/paracetamol drug and/or protein adduct levels may be warranted.

All cases demonstrated on repeat testing as meeting the laboratory criteria of AST/ALT and TBili elevation defined above should be considered potential DILI (Hy's law) cases if no other reason for the LFT abnormalities has yet been found. Such potential DILI (Hy's law) cases are to be reported as SAEs, irrespective of availability of all the results of the investigations performed to determine etiology of the LFT abnormalities.

A potential DILI (Hy's law) case becomes a confirmed case only after all results of reasonable investigations have been received and have excluded an alternative etiology.

16. APPENDIX 6: ECG FINDINGS OF POTENTIAL CLINICAL CONCERN

ECG Findings That May Qualify as AEs

- Marked sinus bradycardia (rate <40 bpm) lasting minutes.
- New PR interval prolongation >280 msec.
- New prolongation of QTcF to >480 msec (absolute) or by \geq 60 msec from baseline.
- New-onset atrial flutter or fibrillation, with controlled ventricular response rate: ie, rate <120 bpm.
- New-onset type I second-degree (Wenckebach) AV block of >30 seconds' duration.
- Frequent PVCs, triplets, or short intervals (<30 seconds) of consecutive ventricular complexes.

ECG Findings That May Qualify as SAEs

- QTcF prolongation >500 msec.
- New ST-T changes suggestive of myocardial ischemia.
- New-onset left bundle branch block (QRS >120 msec).
- New-onset right bundle branch block (QRS >120 msec).
- Symptomatic bradycardia.
- Asystole:
 - In awake, symptom-free patients in sinus rhythm, with documented periods of asystole \geq 3.0 seconds or any escape rate <40 bpm, or with an escape rhythm that is below the AV node;
 - In awake, symptom-free patients with atrial fibrillation and bradycardia with 1 or more pauses of at least 5 seconds or longer;
 - Atrial flutter or fibrillation, with rapid ventricular response rate: rapid = rate >120 bpm.
- Sustained supraventricular tachycardia (rate >120 bpm) ("sustained" = short duration with relevant symptoms or lasting >1 minute).
- Ventricular rhythms >30 seconds' duration, including idioventricular rhythm (heart rate <40 bpm), accelerated idioventricular rhythm (HR 40 bpm to <100 bpm), and

monomorphic/polymorphic ventricular tachycardia (HR >100 bpm (such as torsades de pointes)).

- Type II second-degree (Mobitz II) AV block.
- Complete (third-degree) heart block.

ECG Findings That Qualify as SAEs

- Change in pattern suggestive of new myocardial infarction.
- Sustained ventricular tachyarrhythmias (>30 seconds' duration).
- Second- or third-degree AV block requiring pacemaker placement.
- Asystolic pauses requiring pacemaker placement.
- Atrial flutter or fibrillation with rapid ventricular response requiring cardioversion.
- Ventricular fibrillation/flutter.
- At the discretion of the investigator, any arrhythmia classified as an adverse experience.

The enumerated list of major events of potential clinical concern are recommended as "alerts" or notifications from the core ECG laboratory to the investigator and Pfizer study team, and not to be considered as all inclusive of what to be reported as AEs/SAEs.
17. APPENDIX 7: SNELLEN EQUIVALENCE (VISUAL ACUITY CONVERSION CHART)

| | | | | | Distan | ce | | | | Ne | ar | | |
|----------------|----------------|------------------------|--------|----------------------|-------------|-------------|---------|----------------------|-----------------|----------------------|--------------------|------------------------|-----------------|
| | Visual | Spatial | | % Central | Snellen Eq | uivalent | | % Central | | | Revised | | |
| Line Number | Angle (min) | Frequency (Cyc/deg) | LogMAR | Visual Efficiency | Feet 20/ | Meter 6/ | Decimal | Visual Efficienty | Inches (14/) | Centimeters (35/) | Jaeger Standard | American Point-Type | "M" Notation |
| -3 | 0.50 | 60.00 | 0.30 | 100 | 10 | 3.0 | 2.00 | 100 | 7.0 | 17.5 | - | - | 0.20 |
| -2 | 0.63 | 48.00 | 0.20 | 100 | 12.5 | 3.8 | 1.60 | 100 | 8.8 | 21.9 | - | - | 0.25 |
| -1 | 0.80 | 37.50 | 0.10 | 100 | 16 | 4.8 | 1.25 | 100 | 11.2 | 28.0 | - | - | 0.32 |
| 0 | 1.00 | 30.00 | 0.00 | 100 | 20 | 6.0 | 1.00 | 100 | 14.0 | 35.0 | 1 | 3 | 0.40 |
| 1 | 1.25 | 24.00 | -0.10 | 95 | 25 | 7.5 | 0.80 | 100 | 17.5 | 43.8 | 2 | 4 | 0.50 |
| - | 1.50 | 20.00 | -0.18 | 91 | 30 | 9.0 | 0.67 | 95 | 21.0 | 52.5 | 3 | 5 | 0.60 |
| 2 | 1.60 | 18.75 | -0.20 | 90 | 32 | 9.6 | 0.63 | 94 | 22.4 | 56.0 | 4 | 6 | 0.64 |
| 3 | 2.00 | 15.00 | -0.30 | 85 | 40 | 12.0 | 0.50 | 90 | 28.0 | 70.0 | 5 | 7 | 0.80 |
| 4 | 2.50 | 12.00 | -0.40 | 75 | 50 | 15.0 | 0.40 | 50 | 35.0 | 87.5 | 6 | 8 | 1.0 |
| - | 3.00 | 10.00 | -0.48 | 67 | 60 | 18.0 | 0.33 | 42 | 42.0 | 105.0 | 7 | 9 | 1.2 |
| 5 | 3.15 | 9.52 | -0.50 | 65 | 63 | 18.9 | 0.32 | 40 | 44.1 | 110.3 | 8 | 10 | 1.3 |
| - | 3.50 | 8.57 | -0.54 | 63 | 70 | 21.0 | 0.29 | 32 | 49.0 | 122.5 | - | - | 1.4 |
| 6 | 4.00 | 7.50 | -0.60 | 60 | 80 | 24.0 | 0.25 | 20 | 56.0 | 140.0 | 9 | 11 | 1.6 |
| 7 | 5.00 | 6.00 | -0.70 | 50 | 100 | 30.0 | 0.20 | 15 | 70.0 | 175.0 | 10 | 12 | 2.0 |
| - | 5.70 | 5.26 | -0.76 | 44 | 114 | 34.2 | 0.18 | 12 | 79.8 | 199.5 | 11 | 13 | 2.3 |
| 8 | 6.25 | 4.80 | -0.80 | 40 | 125 | 37.5 | 0.16 | 10 | 87.5 | 218.8 | 12 | 14 | 2.5 |
| - | 7.50 | 4.00 | -0.88 | 32 | 150 | 45.0 | 0.13 | 6 | 105.0 | 262.5 | - | - | 3.0 |
| 9 | 8.00 | 3.75 | -0.90 | 30 | 160 | 48.0 | 0.13 | 5 | 112.0 | 280.0 | 13 | 21 | 3.2 |
| 10 | 10.00 | 3.00 | -1.00 | 20 | 200 | 60.0 | 0.10 | 2 | 140.0 | 350.0 | 14 | 23 | 4.0 |
| 11 | 12.50 | 2.40 | -1.10 | 17 | 250 | 75.0 | 0.08 | 0 | 175.0 | 437.5 | - | - | 5.0 |
| - | 15.00 | 2.00 | -1.18 | 16 | 300 | 90.0 | 0.07 | 0 | 210.0 | 525.0 | - | - | 6.0 |
| 12 | 16.00 | 1.88 | -1.20 | 15 | 320 | 96.0 | 0.06 | 0 | 224.0 | 560.0 | - | - | 6.4 |
| 13 | 20.00 | 1.50 | -1.30 | 10 | 400 | 120.0 | 0.05 | 0 | 280.0 | 700.0 | - | - | 8.0 |
| 16 | 40.00 | 0.75 | -1.60 | 5 | 800 | 240.0 | 0.03 | 0 | 560.0 | 1400.0 | - | - | 16.0 |
| 20 | 100.00 | 0.30 | -2.00 | 0 | 2000" | 600.0 | 0.01 | 0 | 1400.0 | 3500.0 | - | - | 40.0 |
| 30 | 1000.00 | 0.03 | -3.00 | 0 | 200001 | 6000.0 | 0.001 | 0 | 14000.0 | 35000.0 | - | - | 400.0 |

Bold values are standard logMAR progression.

LogMAR = logarithm of the minimum angle of resolution

*20/2000 is equivalent to counting fingers @ 2 feet

120/20000 is equivalent to hand motion @ 2 feet

Holladay J. Visual acuity measurements. J Cataract Refract Surg. 2004;30(2) 297-90.

18. APPENDIX 8: ALTERNATIVE MEASURES DURING PUBLIC EMERGENCIES

The alternative study measures described in this section are to be followed during public emergencies, including the COVID-19 pandemic. This appendix applies for the duration of the COVID-19 global pandemic and will become effective for other public emergencies only upon written notification from Pfizer.

Use of these alternative study measures are expected to cease upon the return of business as usual circumstances (including the lifting of any quarantines and travel bans/advisories).

18.1. Eligibility

While SARS-CoV2 testing is not mandated for this study, local clinical practice standards for testing should be followed. A patient should be excluded if he/she has a positive test result for SARS-CoV2 infection, is known to have asymptomatic infection, or is suspected of having SARS-CoV2. Patients with active infections are excluded from study participation as per Section 5.2 Exclusion Criteria. Active infection requiring systemic therapy.

When the infection resolves, the patient may be considered for re-screening.

18.2. Telehealth Visits

In the event that in-clinic study visits cannot be conducted, every effort should be made to follow up on the safety of study patients at scheduled visits per the Schedule of Activities or unscheduled visits. Telehealth visits may be used to continue to assess patient safety and collect data points. Telehealth includes the exchange of healthcare information and services via telecommunication technologies (e.g., audio, video, video-conferencing software) remotely, allowing the patient and the investigator to communicate on aspects of clinical care, including medical advice, reminders, education, and safety monitoring. The following assessments must be performed during a telehealth visit:

- Review and record study treatment(s), including compliance and missed doses.
- Review and record any AEs and SAEs since the last contact. Refer to Section 7.5.
- Review and record any new concomitant medications or changes in concomitant medications since the last contact.
- Review and record contraceptive method and results of pregnancy testing. Confirm that the patient is adhering to the contraception method(s) required in the protocol. Refer to Appendix 1 and Section 18.3.1 of this appendix regarding pregnancy tests.

Study patients must be reminded to promptly notify site staff about any change in their health status.

18.3. Alternative Facilities for Safety Assessments

18.3.1. Laboratory Testing

If a study patient is unable to visit the site for protocol-specified safety laboratory evaluations, testing may be conducted at a local laboratory if permitted by local regulations. The local laboratory may be a standalone institution or within a hospital. The following safety laboratory evaluations may be performed at a local laboratory:

• Refer to Section 7.3.9 Clinical Safety Laboratory Assessments, Table 11 for the list of safety laboratory evaluations, including pregnancy testing required per protocol.

If a local laboratory is used, qualified study site personnel must order, receive, and review results. Site staff must collect the local laboratory reference ranges and certifications/ accreditations for filing at the site. Laboratory test results are to be provided to the site staff as soon as possible. The local laboratory reports should be filed in the patientt's source documents/medical records. Relevant data from the local laboratory report should be recorded on the CRF.

If a patient requiring pregnancy testing cannot visit a local laboratory for pregnancy testing, a home urine pregnancy testing kit with a sensitivity of at least 25 IU/mL may be used by the patient to perform the test at home, if compliant with local regulatory requirements. The pregnancy test outcome should be documented in the patient's source documents/medical records and relevant data recorded on the CRF. Confirm that the patient is adhering to the contraception method(s) required in the protocol.

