- Left ventricular dysfunction: Symptomatic or asymptomatic decreases in ejection fraction occurred in 7% of patients, with Grade 3 left ventricular dysfunction occurring in 1.6% of patients.
- Hemorrhage: Hemorrhage occurred in 19% of patients, with events ≥ Grade 3 occurring in 3.2% of patients. Fatal intracranial hemorrhage in the setting of new or progressive brain metastases occurred in 1.6% of patients. The most frequent hemorrhagic events were gastrointestinal, including rectal hemorrhage (4.2%), hematochezia (3.1%), and hemorrhoidal hemorrhage (1%).
- Venous thromboembolism: Occurred in 6% of patients, including 3.1% of patients who developed pulmonary embolism.
- **Ocular toxicities:** Serous retinopathy is a class effect of MEK inhibitors. It is generally asymptomatic or mildly symptomatic and reversible (Urner-Bloch et al, 2016). Serous retinopathy occurred in 20% of patients. Symptomatic serous retinopathy occurred in 8% of patients with no cases of blindness. The median time to onset of the first event of serous retinopathy (all grades) was 1.2 months. RVO is a known class-related adverse reaction of MEK inhibitors and may occur in patients treated with binimetinib in combination with encorafenib. In patients with *BRAF* mutation-positive melanoma across multiple clinical trials, 0.1% of patients experienced RVO.
- **Pneumonitis/Interstitial Lung Disease**: Pneumonitis occurred in 0.3% of patients with *BRAF* mutation-positive melanoma across multiple clinical trials.
- **Hepatotoxicity:** The incidence of Grade 3 or 4 increases in liver function laboratory tests was 6% for ALT, 2.6% for AST and 0.5% for alkaline phosphatase. No patient experienced Grade 3 or 4 serum bilirubin elevation.
- **CK Elevation/Rhabdomyolysis**: Asymptomatic elevations of laboratory values of serum CK occurred in 58% of patients. Rhabdomyolysis was reported in 0.1% of patients with *BRAF* mutation-positive melanoma across multiple clinical trials.

- **QTc Prolongation:** QT prolongation has been observed in patients treated with BRAF inhibitors. Encorafenib is associated with dose-dependent QTc interval prolongation in some patients. In the COLUMBUS study, an increase in QTcF to > 500 ms was measured in 0.5% of patients.
- **Embryo-Fetal Toxicity:** Encorafenib or binimetinib can cause fetal harm when administered to pregnant women.

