- 13. Female patients of childbearing potential as described in Appendix 1, must have a negative serum β HCG test result.
- 14. Female patients of childbearing potential must agree to use methods of contraception that are highly effective or acceptable, as described in Appendix 1, and to not donate ova from Screening until 30 days after the last dose of study treatment.

15. Male patients must agree to use methods of contraception that are highly effective or acceptable, as described in Appendix 1, and to not donate sperm from Screening until 90 days after the last dose of study drug.

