7.3.9.2. Pregnancy Testing

Pregnancy testing (serum and urine) as outlined in the SoA (Table 3) will only be required for women of childbearing potential as defined in Appendix 1. Serum pregnancy tests will be performed centrally, and urine pregnancy tests will be performed locally. Pregnancy testing (serum or urine) should be repeated as medically indicated (e.g., in case of loss of menstrual cycle, when pregnancy is suspected), or per country-specific requirement (note that countryrequired urine pregnancy testing will be outlined and communicated to the investigational sites under separate cover). All blood and urine collections for pregnancy tests occurring on dosing days (i.e., Day 1 of each cycle) must be performed with results available prior to study treatment administration.

If a urine pregnancy test is positive, the results will be confirmed with a serum pregnancy test. If the serum pregnancy test is negative after a urine test was positive, the Investigator will assess the potential benefit/risk to the patient and determine whether it is in the patient's best interest to resume study treatment and continue participation in the study. If pregnancy is confirmed by a serum pregnancy test, see Section 7.5.5 for reporting requirements.

Patients of nonchildbearing potential as defined in Appendix 1 do not require pregnancy tests.

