• Females on HRT and whose menopausal status is in doubt will be required to use one of the non-estrogen hormonal highly effective contraception methods if they wish to continue their HRT during the study. Otherwise, they must discontinue HRT to allow confirmation of postmenopausal status before study enrollment.

Contraception Guidance:

NOTE: There is a potential for encorafenib to induce CYP3A4, which may reduce the effectiveness of hormonal contraception methods. Therefore, the use of at least 1 form of non-hormonal contraception is required for females of childbearing potential during participation in this study.

The contraception guidelines outlined below are adapted from the recommendations related to contraception and pregnancy testing in clinical trials guidance document (Clinical Trials Facilitation Group Guidelines 2014). Patients must agree to use highly effective methods of contraception if it is mandated locally or when, in the judgment of the Investigator, compliance with acceptable methods is likely to be suboptimal. Any of the contraceptive methods listed below are permitted on the study and should be communicated to patient and their understanding confirmed.

The following methods have been classified as being highly effective (i.e., failure rate < 1% per year when used consistently and correctly) in preventing a pregnancy:

- Complete abstinence from heterosexual intercourse during the entire period of risk associated with the study treatments; the reliability of sexual abstinence should be evaluated in relation to the duration of the clinical trial and the preferred and usual lifestyle of the patient
- Combined (estrogen and progestogen containing) hormonal contraception associated with inhibition of ovulation:
 - o Oral.
 - o Intravaginal.
 - Transdermal.
- Progestogen-only hormonal contraception associated with inhibition of ovulation:
 - o Oral.
 - Injectable.
 - Implantable.
- Intrauterine device (IUD).
- Intrauterine hormone-releasing system (IUS).

- Bilateral tubal occlusion.
- Vasectomised partner (considered highly effective provided the vasectomized male has received medical assessment of surgical success and that the male is a female patient's sole sexual partner).

Acceptable birth control methods characterized as having a failure rate of more than 1% per year include:

- Progestogen-only oral hormonal contraception, where inhibition of ovulation is not the primary mode of action.

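### Protocol Section 18.3.1 sets the home pregnancy-kit sensitivity at 25 IU/mL (25,000 mIU/mL), probably a unit slip, so as printed it would not exclude an inadequate kit

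*Protocol*

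**What the plan says.** Appendix 8 of the protocol sets out alternative measures for public emergencies. Its introduction limits the scope: "This appendix applies for the duration of the COVID-19 global pandemic", and it extends to other emergencies only when the sponsor gives written notice. Within it, Section 18.3.1 first allows safety laboratory tests, including pregnancy tests, to move to a local laboratory. The home kit is the next step down: "If a patient requiring pregnancy testing cannot visit a local laboratory for pregnancy testing", then "a home urine pregnancy testing kit with a sensitivity of at least 25 IU/mL may be used by the patient", provided that this complies with local regulatory requirements. The result is recorded, and the site is told: "Confirm that the patient is adhering to the contraception method(s) required in the protocol".

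The regular rule is in Section 7.3.9.2: "All blood and urine collections for pregnancy tests occurring on dosing days (i.e., Day 1 of each cycle) must be performed with results available" before study treatment is given. The same section calls for a serum test after a positive urine test, and for repeat testing when medically indicated. The Schedule of Activities (Table 3) lists serum tests at screening and end of treatment, and urine tests on Day 1 of each cycle. At entry, women of childbearing potential "must have a negative serum β HCG test result" (Section 5.1). Section 2.1.4 states the risk: "Encorafenib or binimetinib can cause fetal harm when administered to pregnant women".

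**The concern.** A sensitivity requirement in a protocol exists to keep inadequate kits out. Here the number is in IU/mL, and at face value it accepts a kit that stays negative until hCG reaches 25,000 mIU/mL. A site has nothing in the protocol or SAP to check it against, because no other pregnancy test in either document carries a detection limit.

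The patients concerned may be seen by telehealth (Section 18.2) or home health visit (Section 18.5), both of which refer back to Section 18.3.1 for pregnancy testing. Section 18.4 allows study drug to be couriered to them. For such a patient the home kit may be the only scheduled pregnancy test in a cycle. What is at stake is late recognition of a pregnancy during exposure to two drugs with a stated fetal risk.

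**Working it through.** **Inputs.** The limit of 25 IU/mL comes from Protocol Section 18.3.1. The factor 1 IU = 1,000 mIU is the meaning of the prefix. The documents give no detection limit for a usable urine test, so I assume 10 to 100 mIU/mL and show the range. The 25 IU/mL is a bare specification with no inputs behind it, so there is no plan calculation to reproduce.

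**Step 1: conversion.** 25 IU/mL × 1,000 = 25,000 mIU/mL.

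**Step 2: ratio of the printed limit to an assumed usable limit.** Ratio = 25,000 ÷ assumed limit.

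| Assumed usable limit (mIU/mL) | Ratio |
|---|---|
| 10 | 2,500 |
| 20 | 1,250 |
| 25 | 1,000 |
| 50 | 500 |
| 100 | 250 |

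The printed limit is more than two orders of magnitude too lax throughout. The row at 25 is also what a lost prefix would imply: the same digits in mIU/mL, exactly 1,000 times lower than printed.

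**Step 3: the two readings of *at least*.** Let L be the lowest concentration that a kit detects.

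- As a minimum performance, the criterion is L ≤ 25,000 mIU/mL. A kit with L = 25,000 complies, and so does one with L = 25.
- As a literal number, the criterion is L ≥ 25,000 mIU/mL. A kit with L = 25,000 complies, and one with L = 25 does not.

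The first reading is the more natural. Under both, a kit that stays negative until 25,000 mIU/mL is acceptable.

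**Step 4: what follows a false-negative home result.** Section 7.3.9.2 sends a positive urine result to serum confirmation and has no matching step after a negative one. Table 3 has no routine serum test between screening and end of treatment. What remains is the next Day 1 test, plus repeat testing when medically indicated, for example after a missed menstrual period or when pregnancy is suspected.

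**The case against.** The strongest reply is that the practical effect is unproven and probably small. The provision is a fallback behind both the site and a local laboratory, and it is confined to emergencies. On the natural reading of *at least*, a sensitive kit complies, and nothing shows that an insensitive one would be supplied. Local regulatory compliance is a second condition on the kit. Other safeguards continue: the entry serum test; contraception, of which Appendix 1 says "the use of at least 1 form of non-hormonal contraception is required for females of childbearing potential during participation in this study"; adherence checks at telehealth and home visits and alongside the kit; and repeat testing on suspicion. All of this stands and limits the reach. None of it makes the printed figure a working limit.

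The reply is also right about several stronger conclusions that a reader might draw:

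- **That the kit is 1,000 times too insensitive, as a fact.** The factor depends on an outside benchmark. Only the assumed range of 250 to 2,500 can be given.
- **That the error delays detection by a stated number of days or one cycle.** This needs an hCG growth rate that the documents do not give, and it ignores repeat testing when medically indicated.
- **That a negative home result releases the next supply of drug.** Section 7.3.9.2 requires results to be available before treatment. After a positive urine and a negative serum test it leaves resumption to the investigator. Section 18.3.1 says only that the outcome is recorded and contraception adherence confirmed.
- **That the plan leaves patients unprotected against fetal exposure.** The safeguards above contradict this.

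**Conclusion.** The point holds in a limited form. The limit in Section 18.3.1 equals 25,000 mIU/mL, and as printed it would not exclude an inadequate kit. That conversion is exact. The size of the shortfall, 250 to 2,500 times, rests on the assumed usable limit of 10 to 100 mIU/mL. A slip of IU for mIU is the likely explanation, but that judgement rests on the same assumption and cannot be proved from the documents.

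The affected group is women of childbearing potential who can reach neither the site nor a local laboratory under Appendix 8. Their number is unknown. Sample size, type I error, power and every efficacy analysis are untouched. The correction is still worth making, because the figure is an operative safety criterion, a false negative leads to no serum check, and the protocol itself states the fetal risk.

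**What to change.** The sponsor's laboratory group should verify the intended unit. Section 18.3.1 should then state a maximum detection limit in place of a minimum sensitivity, in a form such as: able to detect hCG at X mIU/mL or lower, with X confirmed by that group. If only the unit prefix was dropped, X is 25. This settles both the unit and the direction. It would also help to say whether the same limit applies to the locally performed urine tests in Section 7.3.9.2, which have none.

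The cost is one phrase in the protocol and a note to sites. No analysis or SAP text changes.
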